Procedures were approved by the Institutional Review Board at the University of Nevada, Reno. Electronic parental consent was obtained when the child was under the age of 18, in which case child assent was also obtained. Participants 18 and older provided electronic consent. Participants were recruited with flyers at a regional diabetes camp, flyers to community diabetes support groups, and direct recruitment by research staff in a local pediatric endocrinology clinic to obtain participants from both urban and rural areas of Nevada. Recruitment for this parallel pilot trial began in the fall of 2018 and completed in early spring 2020. All enrolled participants completed a baseline survey and were randomized to either begin the 10-week intervention period immediately or in 10-weeks. Based on prior studies of predictors of glycemic levels and treatment response, randomization was computerized and stratified based on gender, length since type 1 diabetes diagnosis (at or below 2 years versus more than 2 years) and most recent HbA1c (at or below 8.5% versus at or above 8.6%). After the baseline assessment and across the initial and waitlist intervention periods, participants also completed assessment questionnaires 10 weeks and 20 weeks after the study start date.

Research staff were trained by two graduate students on recruitment procedures and eligibility criteria. Sixty-four participants contacted our research staff indicating interest in participating in the study and provided permission to contact either online or in person (See Figure 1). During the study period, an interim study endpoint was reached where it was determined due to attrition and loss to follow-up as well as feedback from the enrolled participants ($n = 29$) that the intervention required revision to increase acceptability. Thus, enrollment was stopped prior to reaching the planned, per a priori power analyses, sixty participants. Of the 64 participants that indicated interested in the study, five participants

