declined further screening and two participants were not eligible after screening. At the interim stop point, 29 participants had been consented and enrolled in the study. An additional 28 participants expressed interest in enrolling but did not complete the consent process before the interim study endpoint was reached. Among the 29 enrolled participants, 25 participants completed their baseline survey and were randomized to intervention now (n=15) or waitlist (n=10); groups were not balanced as enrollment was stopped early. Four of the 29 participants passively declined to complete the baseline survey and were not randomized. During the course of the study, two participants withdrew from the study after intake (reasons: busy with school, study participation was stressful), but nine were lost to follow-up at 10-weeks and another six were lost to follow-up at 20-weeks.

Intervention Program. The mindfulness-based intervention in the present study was delivered via a teen MBSR workbook and online communication across the 10-week intervention period. Participants were assigned weekly readings and activities from an MBSR workbook for teens (Biegel, 2017). Topics included understanding stress, introduction to mindfulness, mindful eating and other mindfulness-based principles and were recommended to be completed daily. Mindfulness-based exercises were either self-led per instructions provided in the workbook or to be completed using an audio recording directing participants' behaviors. Participants received emails twice per week with reminders about their assignments for the upcoming week and reminders to practice mindfulness daily. At the end of the week, participants received a reminder to complete a brief survey to obtain qualitative data regarding the acceptability of that week's content. Qualitative feedback regarding participants' acceptability of the workbook were used in analyses and included open-ended questions

regarding how helpful participants found each exercise and what hindered them from completing the exercises.

Participants could earn \$10 for each assessment questionnaire, \$10 for completing at least six of the ten weekly survey over the ten-week intervention period, and an additional \$10 for completing all 10 weekly surveys. Maximum earning for each participant was \$50. All measures were completed electronically through RedCap.

Measures

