To further consider the potential utility of the self-led MBSR intervention in this population, the investigators examined changes in the primary outcomes of mindfulness and diabetes related-stress at baseline and 10-week follow-up between the intervention and waitlist groups using independent sample t-tests and from pre-to post-intervention in high engagement participants (those who completed at least six of 10 weekly surveys) using paired sample t-tests. To limit bias from missing data at 10-week follow-up ($n = 11$) in independent sample t-tests an intent-to-treat approach was used, where the baseline level of mindfulness and diabetes-stress was used as the 10-week level for missing data rather than excluding those participants from analyses. The same intent to treat approach was used for the assessment of pre-to post-intervention changes in high engagement participants using paired sample t-tests.

References

Biegel, G. M. (2017). *The stress reduction workbook for teens: Mindfulness skills to help you deal with stress*. New Harbinger Publications.

Brown, K. W., & Ryan, R. M. (2003). The benefits of being present: Mindfulness and its role in psychological well-being. *Journal of Personality and Social Psychology*, 84(4), 822–848.
<https://doi.org/10.1037/0022-3514.84.4.822>

Brown, K. W., West, A. M., Loverich, T. M., & Biegel, G. M. (2011). Assessing adolescent mindfulness: Validation of an Adapted Mindful Attention Awareness Scale in adolescent normative and psychiatric populations. *Psychological Assessment*, 23(4), 1023–1033.
<https://doi.org/10.1037/a0021338>

Delamater, A. M., Patiño-Fernández, A. M., Smith, K. E., & Bubb, J. (2013). Measurement of diabetes stress in older children and adolescents with type 1 diabetes mellitus. *Pediatric Diabetes*, 14(1), 50–56. <https://doi.org/10.1111/j.1399-5448.2012.00894.x>

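### The between-arm t-tests on mindfulness and diabetes stress use no baseline covariate, and the SAP does not settle whether change scores or visit scores were tested; a baseline-adjusted ANCOVA is a cheap, modest improvement

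*Combined protocol and SAP*

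**What the plan says.** The last paragraph of section 2 (Statistical Analysis Plan) holds the only between-arm comparison. The investigators examined "changes in the primary outcomes of mindfulness and diabetes related-stress at baseline and 10-week follow-up between the intervention and waitlist groups" by independent-sample t-tests. The outcomes are mindfulness (MAAS-A) and diabetes stress (DSQ), as defined under Measures. No covariate is named: neither the baseline score nor the three stratification factors given under Procedures (gender, time since diagnosis, HbA1c).

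For the 11 participants without week-10 data, "the baseline level of mindfulness and diabetes-stress was used as the 10-week level for missing data". The only other test of these outcomes is a paired t-test within high-engagement participants, which does not compare arms.

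The paragraph opens with its purpose: "To further consider the potential utility of the self-led MBSR intervention in this population". Procedures reports 15 randomised to intervention and 10 to waitlist, and explains that "groups were not balanced as enrollment was stopped early".

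**The concern.** Two things are open.

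- **The variable.** The word *changes* points to a t-test on change from baseline. The reference to both time points also allows a separate t-test at each visit. The carry-forward rule supplies a week-10 level, which fits either reading. A later sentence, "The same intent to treat approach was used for the assessment of pre-to post-intervention changes in high engagement participants", also speaks of changes, but it describes the paired analysis and is weak evidence about the between-arm one.
- **The baseline score.** On neither reading is it a covariate. A change score subtracts the whole baseline difference and so over-corrects when the correlation is below 1. A 10-week score does not correct at all. The two readings therefore err in opposite directions for the same chance imbalance.

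At stake is how a reader interprets the trial's only randomised comparison of what the SAP calls its primary outcomes. Without knowing the variable, the reader cannot tell which way an imbalance would have pushed the result.

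**Working it through.** **Inputs from the documents.** Arms of 15 and 10 (15 + 10 = 25). Missing at 10 weeks: 2 withdrew and "nine were lost to follow-up at 10-weeks", so 2 + 9 = 11, which agrees with the n = 11 in the SAP; 11/25 = 0.44. The split of the 11 by arm is not given.

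**Assumptions.** Baseline to week-10 correlation r = 0.4 to 0.8; equal SDs, scaled to 1; normal scores; dropout unrelated to the scores; two-sided 5% tests; a true effect of 0.8 SD for power. The documents give none of these.

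**Chance imbalance.** SE of the baseline difference = sqrt(1/15 + 1/10) = 0.408 SD. P(|difference| > 0.5 SD) = 2 × [1 - Phi(0.5/0.408)] = 0.22. This treats allocation as unstratified. Stratification on gender, duration and HbA1c could make imbalance less common if those factors relate to MAAS-A or DSQ.

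**Shift for a +0.5 SD imbalance (intervention higher).** The slope of the week-10 score on baseline is r in those observed and 1 in those carried forward. The average slope is 0.44 + 0.56r.

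| | r = 0.4 | r = 0.5 | r = 0.8 |
|---|---|---|---|
| 10-week score: 0.5 × (0.44 + 0.56r) | +0.332 | +0.360 | +0.444 |
| Change score: 0.5 × (0.56r - 0.56) | -0.168 | -0.140 | -0.056 |
| ANCOVA (simulated) | about 0 | about 0 | about 0 |

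Simulated values agree within about 0.01. With 5/15 v 6/10 to 9/15 v 2/10 missing, ANCOVA stays within 0.03 of zero.

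**Power for 0.8 SD, 11 of 25 carried forward at random (simulated).**

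| | 10-week score | Change score | ANCOVA |
|---|---|---|---|
| r = 0.5 | about 16% | 23-24% | 25% |
| r = 0.8 | about 16% | 46% | 46% |

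Carry-forward is why the gain over the change score is so small. With complete data at r = 0.5, the figures would be 47% for the change score and 58% for ANCOVA. Carry-forward also shrinks the 0.8 SD effect to 0.8 × 14/25 = 0.448 SD under all three analyses.

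**Type I error.** A carried-forward change is exactly 0, so an arm's change-score variance is roughly its observed share times 2(1 - r). What matters is the realised split. In units of 2(1 - r):

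- 9/15 v 2/10 missing gives arm variances 0.4 and 0.8. The true variance of the difference is 0.4/15 + 0.8/10 = 0.107. The pooled formula gives [(14 × 0.4 + 9 × 0.8)/23] × (1/15 + 1/10) = 0.093, which is too small.
- 5/15 v 6/10 missing gives 0.667 and 0.4. The true variance is 0.084 and the pooled formula gives 0.094, which is too large.

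Simulated rates for the pooled change-score t-test (40,000 trials per setting):

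| Missing, intervention v waitlist | Type I error |
|---|---|
| 5/15 v 6/10 | about 3.5% |
| 7/15 v 4/10 | about 5% |
| 9/15 v 2/10 | about 7% |
| 11/15 v 0/10 | about 9% |

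Ordinary ANCOVA behaves similarly (about 4% at the first split, 6.5% at the third). The 10-week t-test stays near 5% at every split. Welch on the change score gives about 4 to 5.5%, and ANCOVA with HC2 standard errors about 4.5 to 6.3%.

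**The case against.** The strongest case is that, on the likelier reading, this is close to a preference. The change score already uses baseline, ANCOVA adds at most a point or two of power, and the illustrated shift (-0.17 to -0.05 SD) is smaller than the estimate's own null SD (0.19 at r = 0.8, 0.31 at r = 0.5). The larger shifts and the real power gain belong to the less likely reading, and there a baseline t-test would at least show the imbalance to the reader. The comparison is exploratory, and the decision to revise the intervention was made "due to attrition and loss to follow-up as well as feedback from the enrolled participants", not on these tests. All of this stands and keeps the severity modest.

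It does not remove the point. The SAP itself calls these the primary outcomes, the variable is not settled, and the adjustment uses data already collected.

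Stronger readings also fail. A reader might infer that an unadjusted t-test is invalid; randomisation supports it without a covariate. A reader might infer that the error rate is near 5% only if dropout is unrelated to arm. That is wrong: the 10-week t-test holds at every split, and the pooled change-score test depends on the split that occurred, whatever its cause. Since the documents give no split, they do not show that any error rate was inflated.

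**Conclusion.** The point holds as a modest improvement. The SAP compares arms only by t-tests without baseline adjustment and leaves the tested variable open between two analyses that respond to chance imbalance in opposite directions. On the likelier reading the exposure is small and ANCOVA mainly removes the imbalance shift; if visit scores were tested, both the shift and the loss of power are substantial.

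The sizes rest on the assumed correlation, effect size and dropout pattern, and the 22% frequency also ignores the stratified randomisation. A reader might expect ANCOVA to rescue the comparison. It does not: 44% of week-10 values are still carried forward, and the dilution to about 0.45 SD is the same with or without the covariate.

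**What to change.** 1. For each outcome (MAAS-A and DSQ total), add an ANCOVA of the 10-week score on arm and baseline score. Report the adjusted difference with a 95% CI, label it post hoc because the data are in, and show it beside the stated t-test, not in its place.
2. In the same text, say whether that t-test used the change score or the score at each visit, and whether it was pooled or Welch.
3. Give the number of carried-forward values in each arm. If they are uneven, use Welch for the change score and HC2 standard errors for the ANCOVA.

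The cost is a few sentences and one extra model per outcome on existing data. The downsides are one residual degree of freedom and the post hoc label, which limits the added analysis to a supporting role.

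### Baseline is carried forward for 11 of 25 randomised participants (44%) to limit bias, but whether it does depends on an undefended zero-change assumption, and no sensitivity analysis is described

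*Combined protocol and SAP*

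**What the plan says.** The last paragraph of the Statistical Analysis Plan (section 2) describes two sets of t-tests on mindfulness and diabetes-related stress, which it names as primary outcomes. One compares the randomised arms. The other compares pre with post in participants who returned six or more weekly surveys. Their stated purpose is "To further consider the potential utility of the self-led MBSR intervention in this population".

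On missing data it says "To limit bias from missing data at 10-week follow-up", with n = 11 given, and then "in independent sample t-tests an intent-to-treat approach was used". The rule is that "the baseline level of mindfulness and diabetes-stress was used as the 10-week level for missing data rather than excluding those participants from analyses". It extends to the second analysis: "The same intent to treat approach was used for the assessment of pre-to post-intervention changes in high engagement participants using paired sample t-tests".

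The Procedures section of the Study Protocol gives the source of the 11. It reports that "two participants withdrew from the study after intake (reasons: busy with school, study participation was stressful", and that "nine were lost to follow-up at 10-weeks and another six were lost to follow-up at 20-weeks".

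The substitution is therefore disclosed. The only reason given for it is that it avoids excluding people. The text offers no argument that those lost did not change, states no missing-data assumption, and describes no second analysis. Attrition is otherwise examined only as a measure of feasibility and acceptability.

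**The concern.** Analysing people in the arm to which they were randomised is intent-to-treat. Setting their change to zero is a separate assumption, and here it supplies 44% of the 10-week values in the only randomised comparison of the two primary outcomes.

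The documents give some reason not to take any one assumption for granted. The Procedures section links attrition to poor acceptability of the intervention. One of the two withdrawals was because taking part was stressful, and stress is an outcome. Those lost may have improved less than completers, not at all, or got worse. The text does not settle which.

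A reader judging potential utility sees one estimate, is told that the method limits bias, and cannot tell how far the result depends on the fill.

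**Working it through.** **Inputs from the documents.** Randomised: 15 intervention and 10 waitlist (Procedures). Missing at 10 weeks: 11 (Statistical Analysis Plan).

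**The plan's own figure.** 2 withdrawn + 9 lost = 11, which matches. 11/25 = 44%. Observed: 25 − 11 = 14. An ANCOVA with intercept, arm and baseline leaves 14 − 3 = 11 df.

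**Assumptions.** SD 1, baseline to 10-week correlation 0.6, gains counted in the direction of improvement. The text does not give the arm split of the 11, and Figure 1, which may give it, is not shown. Splits are written intervention/waitlist, with 7/4 (close to proportional) as the main case. The plan can be read as testing 10-week scores or change scores, so both are given. Effect sizes are illustrative.

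**Step 1: bias with no waitlist change.** Let m be the missing share in the intervention arm, c the mean gain in completers and g the mean gain in those lost.

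- Truth = (1 − m)c + mg
- Filled estimate = (1 − m)c, so its error is −mg
- Observed-data estimate = c, so its error is m(c − g)

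The fill is unbiased at g = 0. For c > 0 it is less biased than the observed-data estimate when g < c/2, and more biased when g > c/2. With m = 7/15 = 0.467 and c = 0.8, the filled estimate is 0.8 × (1 − 7/15) = 0.43:

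| Gain in those lost | Truth | Filled (0.43) misses by | Observed (0.80) misses by |
|---|---|---|---|
| −0.3 | 0.29 | 0.14 | 0.51 |
| 0 | 0.43 | 0 | 0.37 |
| 0.2 | 0.52 | 0.09 | 0.28 |
| 0.4 | 0.61 | 0.19 | 0.19 |
| 0.8 | 0.80 | 0.37 | 0 |

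**Step 2: interval coverage** (40,000 simulated trials per scenario, 7/4, completers +0.8):

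| Those lost | Truth | Filled 10-week score | Filled change | ANCOVA on 14 observed |
|---|---|---|---|---|
| Gained the same (dropout unrelated to change) | 0.80 | 88% | 77% | 95% |
| Did not change | 0.43 | 96% | 97% | 88% |

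Each method covers properly under its own assumption and falls short under the other's. In the first row the filled interval is centred too low. Its standard error is not understated: for filled change it averages 0.30, against an actual SD of 0.28.

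**Step 3: no effect, both arms drift by 0.5 SD.** With mI and mW the missing shares in the two arms, the false difference is 0.5 × (mW − mI):

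| Split | Arithmetic | False difference | Type I error, change | Type I error, 10-week score |
|---|---|---|---|---|
| 7/4 | 0.5 × (4/10 − 7/15) | −0.03 | about 4% | 4 to 5% |
| 9/2 | 0.5 × (2/10 − 9/15) | −0.20 | about 11% | about 7% |
| 4/7 | 0.5 × (7/10 − 4/15) | +0.22 | about 8% | about 7% |

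At near-proportional missingness the effect is negligible. At uneven missingness the fill is not reliably conservative.

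**The case against.** The strongest defence is that the plan's claim is comparative: filling limits bias relative to excluding. Step 1 shows that this can be true over a wide range, including when those lost worsened. A reader might infer that the fill limits bias only if those lost did not change at all. That is wrong. Zero change is the condition for no bias, not for less bias. The documents' account of low acceptability makes a small gain in those lost quite plausible. The claim should be qualified, not struck out.

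The second defence is noise. The gap of 0.80 − 0.43 = 0.37 SD is smaller than every average 95% half-width at 7/4 and a true 0.8: 0.62 (filled change), 0.88 (filled score) and 0.97 (ANCOVA). In that scenario p < 0.05 occurs in about 25%, 15% and 37% of trials, so any of the three would usually be inconclusive. Nor does either approach win on root-mean-square error. At 7/4 with completers +0.8, filled change against ANCOVA is 0.28 v 0.59 if those lost did not change and 0.46 v 0.45 if dropout is unrelated to change. In the latter case the filled score gives 0.55.

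Third, the effect sizes, drift, correlation and splits are assumed. That is so, and Figure 1 might narrow the splits.

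A reader might also infer that these tests drove the decision to revise the intervention. The Procedures section attributes that decision to attrition and participants' feedback.

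These objections lower the weight and rule out calling the fill wrong. They do not supply the missing justification or a second analysis. The high-engagement paired tests are not a sensitivity analysis, because they use the same fill in a selected subset. Who enters those tests, and at which visits, is a separate question of definition and not evidence about the fill.

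**Conclusion.** The point holds as a low-weight improvement. The plan fills 44% of the 10-week values with baseline and says that this limits bias, without defending zero change or showing what happens under another assumption.

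In the main illustration the same observed data support 0.43 SD or 0.80 SD. Which is nearer the truth turns on whether those lost gained less or more than half of what completers gained. This rests on no waitlist change and an assumed 7/4 split. If both arms drift by 0.5 SD, uneven missingness can create a false difference of about 0.2 SD in either direction.

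The documents do not show that the filled result is biased, that the observed-data result is better, or that the main analysis must change. The weight is low because the tests are a supplementary look at utility in a pilot that was stopped early. The first aim uses baseline data, and feasibility and acceptability rest on attrition, survey counts and feedback.

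**What to change.** 1. Call the fill 'baseline carried forward' and state its zero-change assumption. Keep 'intent-to-treat' for analysis as randomised. Qualify the bias statement as depending on how those lost changed.
2. Keep the filled t-tests. Beside them report an ANCOVA of the observed 10-week score on arm and baseline (14 observed, 11 df) under a stated missing-at-random assumption, with the difference and 95% CI, labelled post hoc.
3. Add a delta-shift table: ANCOVA estimate − mI × dI + mW × dW, where d is the mean change in completers minus the mean change assumed in those lost, by arm. For an ANCOVA estimate of 0.80 at 7/4:
   - (dI, dW) = (0, 0): 0.80
   - (0.2, 0): 0.80 − 0.467 × 0.2 = 0.71
   - (0.4, 0): 0.80 − 0.467 × 0.4 = 0.61
   - (0.4, 0.4): 0.80 − 0.467 × 0.4 + 0.4 × 0.4 = 0.77
   - (0.8, 0): 0.80 − 0.467 × 0.8 = 0.43

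   Setting d to each arm's mean change in completers approximately returns the filled point estimate. State that this row carries the wider ANCOVA interval (half-width about 0.97 SD, against 0.62 or 0.88), so it may not reach the same conclusion as the filled t-test.
4. Draw no conclusion on utility that holds under only one of these assumptions.
5. For the high-engagement paired tests, give the number of filled pairs and the observed-pairs result beside the filled one.

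The cost is some wording and a re-run on data already held. The downsides are a wider interval, an observed-data estimate that is too large if those lost did not improve, and added analyses that were chosen after the data were seen.
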